Title of Study: A Phase I, Randomized, Double-Blind, Placebo-Controlled Study to Evaluate the Safety, Tolerability, and Pharmacokinetics of Single and Multiple Ascending Doses of Inhaled MBS-COV (SNS812) in Healthy Participants	
Study Center: One center in the United States (US)	
Planned Number of Participants: 44 participants	Study Development Phase: Phase I
Indication for Use: MBS-COV is indicated for patients with mild to moderate COVID-19	
<h3>Study Objectives</h3> 
Primary Objective:
 
 • To determine the safety and tolerability of MBS-COV after single and multiple doses in healthy participants. 
Secondary Objective:
 
 • To evaluate the pharmacokinetics (PK) of MBS-COV after single dose administration (Part A) and multiple dose administrations in healthy participants (Part B). • To evaluate the immunogenicity of MBS-COV. 	
<h3>Study Outcome Measures</h3> 
Primary Outcome Measures:
 
The primary outcome measures in this study are:
 
 ○ Evaluation of the safety and tolerability of MBS-COV after a single and multiple dose administrations in healthy participants. The safety and overall tolerability assessments will be evaluated based on: 
 - Incidence and severity of Treatment-Emergent Adverse Events (TEAEs) - Incidence of withdrawals due to Adverse Events (AEs) - Incidence of Treatment-Related Adverse Events - Incidence of Serious Adverse Events (SAEs) - Change/shifts in laboratory values from baseline - Change in vital signs including blood pressure, pulse, respiratory rate, and temperature from baseline - Change in spirometry from baseline to assess the acute bronchospasm 	

Name of Sponsor/Company:

Oneness Biotech Co., Ltd.

Name of Study Product: MBS-COV(SNS812)**Comparator Product:** Placebo (Normal Saline)**Protocol Number:**

SNS812CLCT01

Indication:

Coronavirus Disease 2019 (COVID-19)

- Change in other safety examination parameters from baseline

Secondary Outcome Measures:

The secondary outcome measures in this study are:

Pharmacokinetic Outcome Measures:

- Maximum observed plasma drug concentration (C_{max})
- Apparent terminal elimination half-life ($t_{1/2}$)
- Time to maximum observed plasma drug concentration (T_{max})
- Area under the plasma drug concentration-time curve (AUC) from time 0 to the time of the last quantifiable concentration (T_{last}) (AUC_{0-t})
- AUC from time 0 to infinity ($AUC_{0-\infty}$)
- Apparent plasma clearance (CL/F)
- Estimate of steady state Pharmacokinetic Parameters such as $AUC_{0-\tau}$, and $C_{max,ss}$, $C_{min,ss}$, C_{avg} , T_{max} , $t_{1/2}$, AUC_{tau} , λ_z , CL_{ss}/F , V_{ss}/F , DF, AR_{AUC}/AR_{Cmax} (accumulation ratio) for multiple dose administration of MBS-COV

Immunogenicity Outcome Measure:

- Occurrence of anti MBS-COV antibody (ADA) after administration of MBS-COV

Study Design:

This is a Phase I, randomized, double-blind study designed to evaluate the safety, tolerability and pharmacokinetics (PK) of inhaled MBS-COV in healthy adult participants in the part A and part B of the study. A total of 44 male and female healthy participants will be enrolled. All participants, after signing the Informed Consent Form (ICF), will be assessed during the screening phase. Only those participants who successfully complete the screening phase and meet the study eligibility criteria will be enrolled. MBS-COV will be administered via inhalation through a portable mesh nebulizer.

Part A (SAD phase)

Part A is a randomized, blinded study of a single ascending dose (SAD) phase to evaluate the safety, tolerability and PK of inhaled MBS-COV in healthy participants.

All participants will have a screening visit within 28 days of check-in (Day -1) to determine eligibility. Eligible participants will be admitted to the study center on study Day -1 at which point their eligibility to participate in the study will be confirmed. Only those participants who successfully complete the screening phase and meet the study eligibility criteria will proceed to be randomized to receive a single dose of MBS-COV or placebo in the morning of Day 1 at the assigned dose.

Participants will be assigned to one of up to three doses of MBS-COV (0.3 mg/kg, 0.6 mg/kg, 1.2 mg/kg) and treated sequentially with increasing doses. Each cohort will include eight (8) participants (6 active and 2 placebo) per below table:

Table 0-1: SAD Phase Cohorts

Cohort		Number of Participants	MBS-COV Dose (mg/kg)	Frequency of Dose
SAD Phase	A1	6 (MBS-COV) +2 (placebo)	0.3	Single Administration
	A2	6 (MBS-COV) +2 (placebo)	0.6	Single Administration
	A3	6 (MBS-COV) +2 (placebo)	1.2	Single Administration

SAD phase will include a sentinel design in which 2 participants at the given cohort dose be initially enrolled. If the dose can be well tolerated for 48 hours after full administration per site Principle Investigator's judgement, the remaining 6 participants will be enrolled to receive a single dose of MBS-COV at the same dose.

The decision for the escalation to the higher dose levels will be made by the study SRC after safety review of available information 7-day post treatment period. The data from SAD phase will be reviewed for safety trends to start MAD phase.

Part B (MAD Phase)

This is a randomized, double-blind, placebo-controlled study in approximately 20 healthy participants. Doses will be selected based on a comprehensive review of the SAD data and estimates of the clinically efficacious dose.

The MAD Phase of the study consists of a screening period followed by multiple dose administrations of MBS-COV or placebo through a portable nebulizer once daily for 7 consecutive days (Day 1 to Day 7). Participants will be followed up for 21 days to assess post-treatment safety.

The decision for the escalation to the higher dose levels will be made by the study SRC after safety review

of available information 7-day post treatment period. Each cohort will include ten participants (8 active and 2 placebo) per table below:

Table 0-2: MAD Phase Cohorts

Cohort		Number of Participants	MBS-COV Dose (mg/kg)	Dose
MAD Phase	B1	8 (MBS-COV) +2 (placebo)	0.6	Once daily for 7 days
	B2	8 (MBS-COV) +2 (placebo)	1.2	Once daily for 7 days

Study Visits:

- **Screening Visit (SV: Up to 28 Days prior to Day 1):** Consists of signing the ICF and study qualification based on evaluation of inclusion/exclusion criteria.
- **Treatment Visit 0 (T0: Day -1):** All participants continuing to meet eligibility criteria will be enrolled into the study and confined to research clinic until Day 2 for cohort A1 to A3 (SAD phase) and Day 9 for cohort B1 to B2 (MAD phase).
- **Treatment Visit 1: Baseline Visit (T1: Day 1):** The first assigned study treatment dose will be administered after completion of all study evaluations. Adverse events and changes in concomitant medications will be collected. Participants in Cohorts A1 to A3 will inhaled a single dose of MBS-COV or placebo through a portable nebulizer on Day 1. Participants in cohort B1 and B2 will receive doses of MBS-COV or placebo by through a portable nebulizer once daily for 7 consecutive days from Day 1 to Day 7.

Part A (SAD Phase)

- **Treatment Visit 2 (T2: Day 2)**
- **Treatment Visit 3 (T3: Day 3)**
- **Treatment Visit 4 (T4: Day 4)**
- **Treatment Visit 5 (End of Treatment) (T5: Day 7)**
- **Follow-Up Visit 1 (FU1: Day 14)**
- **Follow-Up Visit 2 (FU2: Day 28)**

Part B (MAD Phase)

- **Treatment Visit 2 (T2: Day 2)**
- **Treatment Visit 3 (T3: Day 3)**
- **Treatment Visit 4 (T4: Day 4)**
- **Treatment Visit 5 (T5: Day 5)**
- **Treatment Visit 6 (T6: Day 6)**
- **Treatment Visit 7 (T7: Day 7)**
- **Treatment Visit 8 (T8: Day 8)**
- **Treatment Visit 9 (End of Treatment) (T9: Day 9)**
- **Follow-Up Visit 1 (FU1: Day 14)**

- **Follow-Up Visit 2 (FU2: Day 28)**

If any of the dose escalation stopping criteria have occurred in Part A or Part B, the SRC will make a final recommendation for dose escalation to the next cohort.

[figure not shown]
NOTE: The dose escalation decision through the study will not be made until the following:

- (1) All study participants in a given cohort have been enrolled,
- (2) All such participants have completed Treatment Visit 5 (Day 7) (for SAD-Part A) and Treatment Visit 9 (Day 9) (for MAD-Part B) of the study or withdrawn from the study, whichever occurs first.
- (3) The SRC will review the available safety data and recommend further dose escalation.

Additionally, dose escalation stopping criteria are defined per the below:

- a. Death in any participant in which the cause of death is judged to be possibly, probably or definitely related to MBS-COV.
- b. The occurrence in any participant of a severe local application site reaction (Grade 3 which doesn't resolve or recurs; or Grade 4) that is judged to be possibly, probably or definitely related to MBS-COV.
- c. The occurrence in any participant of a SAE whose causal relationship to MBS-COV is judged to be probably, possibly, or definitely related to MBS-COV.
- d. The occurrence, in two or more participants of Grade 3 AE or laboratory abnormalities, judged to be probably, possibly, or definitely related to MBS-COV.
- e. The occurrence of two of the same AE or laboratory abnormality \geq Grade 3 judged to be probably, possibly, or definitely related to MBS-COV.
- f. The occurrence, in one or more participants of Grade 4 AE or laboratory abnormalities, judged to be probably, possibly, or definitely related to MBS-COV.
- g. Any pattern of significant symptoms, physical findings, or laboratory abnormalities that, although individually minor, collectively represent a safety concern in the opinion of the investigator and are judged by the SRC to be at least possibly related to MBS-COV.
- h. PK exposure limits of mean AUC of 385.6 h*ng/mL or C_{max} of 141.8 ng/mL for one cohort, whichever comes first.(Single dose: AUC of 386.9 h*ng/mL or C_{max} of 91.7 ng/mL)

The SRC will review the PK data (if applicable) and safety trends of available information 7-day post treatment period of Cohort A1 and A2 (or if study stops prematurely due to safety reasons), to start part B of the study. The starting dose of Part B will be determined by SRC.

Figure 0-1: Dose Escalation Schematic**Blood Sample Collection for the PK study:**

- SAD cohorts A1 to A3:** For the single dose on day 1, blood samples will be collected before dosing, and afterwards at 5 min (± 1 min), 15 min (± 2 min), 0.5 h (± 5 min), 1 h (± 5 min), 2 h (± 5 min), 4 h (± 5 min), 8 h (± 10 min), 10 h (± 10 min), 24 h (± 10 min) and 48 h (± 10 min) (Total 11 samples) after dosing.
- MAD cohort B1 and B2:** Blood samples will be collected on Day 1 and Day 7 before dosing, and afterwards at 5 min (± 1 min), 15min (± 2 min), 0.5 h (± 5 min), 1 h (± 5 min), 2 h (± 5 min), 4 h (± 5 min), 8 h (± 10 min), 10 h (± 10 min) on Day 1; and at 5 min (± 1 min), 15min (± 2 min), 0.5 h (± 5 min), 1 h (± 5 min), 2 h (± 5 min), 4 h (± 5 min), 8 h (± 10 min), 10 h (± 10 min), 24 h (± 10 min) and 48 h (± 10 min) after dosing on Day 7; and before dosing on Day 2 to Day 6 (Total 25 samples). The detailed study schedule and assessments in each visit are provided in [Section 4](#) of the protocol.

Blood Sample Collection for the immunogenicity study:

- Blood Sample will be collected on Day 1 before dosing, Day 14 and Day 28 for SAD and MAD cohorts, and the analysis will be performed when analytic method is well-established.

Study Duration:**Part A****SAD Phase:**

- Screening Period (For SAD Phase Only): Up to 28 days
- Treatment Period: 7 days
 - In-unit: 3 day
- Follow-Up Period: Up to 21 days
- Total Study Duration:** Up to 56 days

Part B**MAD Phase:**

- Screening Period: Up to 28 days

- Treatment Period: 9 days
 - In-unit: 9 days
- Follow-Up Period: Up to 19 days after EOT
- **Total Study Duration:** Up to 56 days

Eligibility Criteria

Inclusion Criteria:

Participants will be eligible for enrollment in the study only if they meet ALL the following criteria at time of Screening:

1. Male or female adults who are between 18 and 55 years old (inclusive).
2. Body mass index (BMI) between 18.0 and 32.0 kg/m² (inclusive).
3. No serious or chronic underlying disease which would adversely affect the study conduct and data interpretation per the investigator.
4. Female participants should have negative results in serum pregnancy test at screening and negative urine pregnancy test at admission (Day -1).
5. Participants with normal spirometry (FEV1 %: 80 % or greater) results at screening or day -1.
6. Both male and female participants and their partners of childbearing potential must agree to use two medically accepted methods of contraception (e.g., barrier contraceptives [male condom, female condom, or diaphragm with a spermicidal gel], hormonal contraceptives [implants, injectables, combination oral contraceptives, transdermal patches, or contraceptive rings], or one of the following methods of birth control [intrauterine devices, tubal sterilization or vasectomy] or must practice complete abstinence from intercourse of reproductive potential from study entry to 3 months after the last day of treatment (excluding women who are not of childbearing potential and men who have been sterilized).
7. Participants should have normal (or abnormal but not clinically significant) laboratory results per the PI's judgement including the hematology, biochemistry, coagulation indices and urinalysis
8. Participants should have a normal (or abnormal but not clinically significant) 12-lead ECG at screening and day -1 and chest X-ray at screening
9. Participants should be willing to cooperate and able to participate in this study, comply with all protocol requirements, and sign an informed consent.
10. Current non-smokers and those who have not smoked within the last 3 months. This includes the use of cigarettes, e-cigarettes, and nicotine replacement products.
11. Nasopharyngeal or nasal swab sample of Participants collected for COVID-19 antigen rapid test at screening and qRT-PCR test on Day -1 should be negative.

Eligibility Criteria

Exclusion Criteria:

Participants meeting ANY of the following criteria at time of Screening will be excluded from enrollment:

1. The participant has a known history of, or a positive test result for, hepatitis B surface antigen (HBsAg), hepatitis C virus (HCV), or human immunodeficiency virus (HIV) at screening.
2. As reported by the participant has severe cardiovascular disease, neurological disease, hematological disease, infectious disease, mental disorder, liver disease, gastrointestinal disease, lung disease, endocrine disease, immune disease or kidney disease, or has a history of the above diseases, or other symptoms known to interfere with the absorption, distribution, metabolism, or excretion of the medicine, or other conditions that the investigator believes will increase the risk

of the participant and might interfere with the study conduct and results interpretation

3. The participant has history or presence of active lung disease (i.e., asthma, chronic obstructive pulmonary disease [COPD], pulmonary fibrosis, hemoptysis, bronchiectasis) or prior intubation due to respiratory failure conditions.
4. The participant has upper respiratory infection within the 3 months prior to the first dose of study drug.
5. Consumed more than 14 units of alcohol per week in the 6 months before screening (1 unit of alcohol = 360 mL of beer or 45 mL of spirits with 40% alcohol content or 150 mL of wine) or have taken alcohol products in the 48 hours prior to administration, or those who have a positive alcohol breath test result at screening and day -1.
6. Unwillingness to abstain from the consumption of any caffeine or alcohol-containing food or drinks that may influence the drug metabolism from 48 hours before administration.
7. History of drug abuse or a positive drug abuse (barbiturates, methamphetamine, benzodiazepines, morphine/opiates, phencyclidine (PCP), amphetamines, tetrahydrocannabinol (THC), methylenedioxymethamphetamine (MDMA), cocaine, methadone, and cotinine) test result at screening and day -1.
8. Female participants who are lactating.
9. Use of prescription or non-prescription drugs, including vaccine within 14 days or 5 half-lives (whichever is longer) prior to the first dose of study drug.
10. The subject has received an experimental agent (vaccine, drug, biologic, device, blood product or medication) within 1 month prior to the first dose of study drug and will receive another experimental agent during the duration of this study.
11. The participant has a history of frequent nose bleeding.
12. Participants with known allergic reactions to the study drug or its excipients.
13. The participant has an acute sinusitis or history of chronic sinusitis, a history of active allergic rhinitis (AR), history of perennial allergic rhinitis (PAR), or current seasonal allergic rhinitis (SAR), or recent viral rhinitis within 2 weeks prior to administration.
14. The participant has Any nasopharyngeal abnormality that may have interfered with nasal absorption, distribution, or study-related evaluations of signs or symptoms (e.g., polyps, septal deviation).
15. Blood donation of more than 400 mL within 3 months before screening or more than 200 mL within 4 weeks before screening or plan to donate blood during study period.
16. Any other clinical condition that, in the Investigator's judgment, would potentially compromise study compliance or the ability to evaluate safety/efficacy.

Statistical Considerations:**Sample Size Determination and Rationale**

The sample size of 44 participants (24 healthy participants in part A and 20 healthy participants in part B) will be used in this study. This sample size is selected based on clinical judgment and not based on statistical power calculation; it is deemed adequate to provide clinically meaningful descriptive results consistent with study objectives.

Randomization and Blinding:

All eligible participants will proceed to be randomized and will be assigned the IP kit. A detailed Randomization plan the block size and all the relevant considerations will be detailed in the randomization plan. The participants will be randomized using a web-based randomization system at Treatment Visit 1 (Baseline) and site personnel will be trained on this system. Only those participants who successfully complete the screening phase and meet the study eligibility criteria will proceed to randomization.

Statistical Analysis Populations

Full Analysis Set (FAS): FAS includes all randomized participants. This analysis set will be used to analyze the disposition, demographic and baseline characteristics of the subjects.

Safety Set (SS): SS includes all the participants who receive the study drug at least once. This population will be used for the analysis of safety parameters.

PK concentration analysis set (PKCS): PKCS includes all randomized participants who receive at least one dose of the study drug and have at least plasma concentration. The PKCS will be used for PK concentration analysis.

PK parameters analysis set (PKPS): PKPS includes all randomized participants who receive at least one dose of the study drug with no major protocol violations or protocol deviations that have a significant impact on PK parameters (C_{max} , AUC, etc.), and have at least one analyzable PK parameter. The PKPS will be used for PK parameters analysis.

Immunogenicity Set (IS): The IS includes all randomized participants who receive at least one dose of the study drug, and have at least one ADA concentration. The IS will be used for immunogenicity analysis.

Statistical Analysis

All collected study data will be presented in participant data listings. All report outputs will be produced using SAS® version 9.4 or a later version in a secure and validated environment.

All data collected will be summarized and analyzed according to the variable type:

- Continuous data summaries will include:
 - Number of observations, mean, standard deviation, median, and minimum and maximum values.
- Categorical data summaries will include:
 - Frequency counts and percentages.

No inferential statistics are planned.

The pharmacokinetic analyses will be performed using Phoenix® WinNonlin 8.3.1 or above.

A Statistical Analysis Plan (SAP) will be developed and approved before the database is locked. The SAP will present the detailed statistical methodology to be used in analyzing the pharmacokinetic and safety data from this study.

TABLE OF CONTENTS

PROTOCOL SYNOPSIS	4
TABLE OF CONTENTS	13
List of Tables.....	18
List of Figures	19
List of Abbreviations.....	20
1 INTRODUCTION AND BACKGROUND	22
1.1. Statement of Intent	22
1.2. Background of the Disease	22
1.3. Name and Description of the Investigational Product.....	23
1.4. Summary of Prior Non-Clinical and Clinical Studies	24
1.4.1. Non-Clinical Studies	24
1.4.2. Clinical Studies.....	29
1.5. Risks / Benefits Assessment.....	29
1.5.1. Systemic Anaphylaxis	29
1.5.2. Pregnancy	29
1.5.3. Venipuncture for Blood Sampling	29
1.5.4. Unknown Risks	29
1.6. Rationale for Study Dose	29
2. STUDY OBJECTIVES AND ENDPOINTS/OUTCOME MEASURES	31
2.1. Study Objectives.....	31
2.1.1. Primary Objective.....	31
2.1.2. Secondary Objective.....	31
2.2. Study Outcome Measures.....	31
2.2.1. Primary Outcome Measures	31
2.2.2. Secondary Outcome Measures	31
3. STUDY DESIGN.....	33
3.1. General Schema.....	33
3.2. Study Center	37
3.3. Study Population	37
3.4. Eligibility Criteria.....	37

3.4.1.	Inclusion Criteria.....	37
3.4.2.	Exclusion Criteria.....	38

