Safety Pharmacology	
 No cytotoxicity was observed in the treatment up to 40μM of MBS-COV. No inflammation-associated cytokines were significantly induced in MBS-COV treated-human PBMCs. MBS-COV does not activate non-specific immune response against SASR-CoV-2 in mice treated with efficacy dose of MBS-COV. MBS-COV inhibits viral RNA amplification and infectious virion production, while control siRNA does not. The virus inhibition of MBS-COV is not evoked through nonspecific immune responses. No significant immune stimulation was observed in mice treated with high dose (up to 75 mg/kg) of MBS-COV. No MBS-COV-related changes in cardiovascular functions, respiratory functions, blood pressure, body temperature and clinical observation after administration up to the highest dose of 16+30

Study	Summary
	mg/kg (AI+SC).
Pharmacokinetics	
Lung distribution and pharmacokinetics of MBS-COV in lungs of golden hamsters
 
 • In a single inhalation of MBS-COV at delivered doses of 15.7 and 52.7 mg/kg, MBS-COV level in lungs of golden hamsters peaked at 0.5-1 hr postdose. • The elimination $T_{1/2}$ ranged 60.95 -74.16 hours in low dose group and 152.20 - 182.59 hours in high dose group. • The C_{max} were within 28.98 -30.79 $\mu\text{g/g}$ lung in low dose group and 64.30 - 108.77 $\mu\text{g/g}$ lung in high dose group. • No significant gender difference was found. • The maximum concentrations in lung tissue and the systemic exposures to MBS-COV were positively correlated with the administrated doses. 
Toxicokinetics of MBS-COV in the blood of golden hamsters
 
 • In the 7-day repeat-dose toxicokinetic study, the actual delivered doses were 30 and 90.4 mg/kg for medium and high dose group. The elimination $T_{1/2}$ values ranged from 1.97 to 17.42 hours for sense and antisense strand of MBS-COV in medium and high dose group on Day 1. On Day 7, $T_{1/2}$ values ranged from 1.88 to 6.06 hours. Mean C_{max} and AUC_{last} values increased with the increasing administered doses. MBS-COV did not accumulate in golden hamsters, and there was no significant gender difference. • In the 14-day repeat-dose toxicokinetic study, the actual delivered doses were 57 and 87.9 mg/kg for medium and high dose group. The elimination $T_{1/2}$

Study	Summary

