6. STUDY TREATMENT

6.1. MBS-COV

The investigational product (IP) in this study is MBS-COV. MBS-COV is a sterile, excipient-free lyophilized powder with 50 mg of siRNA in a single dose 2-mL vial, to be reconstituted with normal saline before use for inhalation only at a to-be-determined dose level in milligram/kilogram per day, once daily, for 1 day or 7 consecutive days during this study. MBS-COV drug substance were manufactured at CCI [REDACTED]. The study drug is only formulated with water for injection (WFI), then sterile filtration and lyophilization.

To administer the IP in all cohorts, MBS-COV powder is reconstituted with normal saline (0.9% Sodium Chloride Injection) before use and administered through a portable nebulizer, Vibrating mesh nebulizer Air Pro 3, for single dose groups and multi-dose groups.

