8.7.7. Pharmacokinetic (PK) Analysis

The pharmacokinetic analyses and estimation of PK parameters will be performed using non compartmental methods using Phoenix® WinNonlin 8.3.1 or above.

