4.2.2. Secondary Outcome Measures

The secondary outcome measures in this study are:

Pharmacokinetic Outcome Measures:

- Maximum observed plasma drug concentration (C_{max})
- Apparent terminal elimination half-life ($t_{1/2}$)
- Time to maximum observed plasma drug concentration (T_{max})
- Area under the plasma drug concentration-time curve (AUC) from time 0 to the time of the last quantifiable concentration (T_{last}) (AUC_{0-t})
- AUC from time 0 to infinity ($AUC_{0-\infty}$)
- Apparent plasma clearance (CL/F)
- Estimate of steady state Pharmacokinetic Parameters such as AUC_{0-t} , and $C_{max,ss}$, $C_{min,ss}$, C_{avg} , T_{max} , $t_{1/2}$, AUC_{tau} , λ_z , CL_{ss}/F , V_{ss}/F , DF, AR_{AUC}/AR_{Cmax} (accumulation ratio) for multiple dose administration of MBS-COV

Immunogenicity Outcome Measure:

- Occurrence of anti MBS-COV antibody after administration of MBS-COV

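### The Part B PK list names V_ss/F, which non-compartmental analysis of inhaled-only data cannot estimate; it should be V_z/F, with the day and AUC for Part B clearance stated

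*Protocol*

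**What the plan says.** The synopsis and Protocol 2.2.2 list single-dose type parameters (including AUC0-inf and CL/F) once for the whole study. A further bullet of steady-state parameters ends "V_{ss}/F , DF, AR_{AUC}/AR_{Cmax} (accumulation ratio) for multiple dose administration of MBS-COV" and also contains AUC_tau, lambda_z and CL_ss/F. SAP 4.2.2 repeats the whole set under Part B, so AUC0-inf and CL/F stand there beside CL_ss/F. Neither document gives a formula for V_ss/F, or a day and AUC denominator for Part B CL/F.

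On route, Protocol 6.1 describes the product as "to be reconstituted with normal saline before use for inhalation only", and no cohort in Tables 3-1 or 3-2 is intravenous. On method, Protocol 8.7.7 says "estimation of PK parameters will be performed using non compartmental methods".

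Part B has two PK profiles. Day 1 runs to 10 h, followed by the Day 2 pre-dose sample at 24 h. Day 7 runs to 48 h. SAP 4.4, 7.2.3 and 7.5 defer PK endpoints, data handling and analysis to a separate PK SAP, which is not among the documents.

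**The concern.** V_ss is clearance times the mean residence time (MRT) of drug once it is in the body. After inhalation, the observed residence time also contains the mean absorption time (MAT). Without intravenous data, non-compartmental analysis cannot separate the two. The plan therefore promises a secondary outcome that the design cannot deliver under that name. A reader of the report could take slow entry from the lung for wide distribution in the body.

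The clearance entries raise a smaller question. Day 7 is the longer profile, so it is a natural one to extrapolate to infinity, but its AUC0-inf also contains drug left over from six earlier doses. If Dose/AUC0-inf were taken from Day 7, the report would show two Part B clearances that differ only through carry-over. The difference could be misread as clearance changing with time.

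**Working it through.** **Plan's own figure.** The documents give no value for V_ss/F or CL/F. The nearest stated figure, 25 PK samples in Part B, reproduces: 9 (Day 1) + 5 (Days 2 to 6) + 11 (Day 7) = 25.

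**Inputs.** Dosing interval 24 h and 7 doses (Protocol 3.1). Hamster blood half-lives from Protocol Table 1-1: 1.88 to 6.06 h on Day 7 of the 7-day study, 3.47 to 9.02 h on Day 14 of the 14-day study, and Day 1 maxima of 17.42 h and 36.67 h. The documents give no human half-life and no absorption half-life, so all human values are assumptions. The model is one compartment, linear, with first-order absorption.

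**Volume computed from MRT.** (CL/F) x MRT = (CL/F) x (MRT of disposition + MAT) = V_ss/F + (CL/F) x MAT. The ratio to the true value is 1 + MAT/MRT of disposition. In this model MAT = t_abs/ln 2 and MRT of disposition = t_elim/ln 2, so the ratio is 1 + t_abs/t_elim.

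For t_elim = 9.02 h, the table gives the formula and a noise-free non-compartmental analysis on the planned Day 7 sampling times (linear-log rule, lambda_z from the last three points):

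| Absorption half-life | Formula | V_ss/F from MRT | V_z/F = (CL_ss/F)/lambda_z |
|---|---|---|---|
| 1 h | 1 + 1/9.02 = 1.11 | 1.13 | 1.01 |
| 4 h | 1 + 4/9.02 = 1.44 | 1.50 | 1.17 |
| 9 h | 1 + 9/9.02 = 2.00 | 2.16 | 1.79 |

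Entries are multiples of the true volume. CL_ss/F from AUC_tau stayed within 3% of true in all three rows.

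A shorter elimination half-life makes the ratio larger for the same absorption: 1 + 1/2 = 1.50 at 2 h with 1 h absorption. When absorption is slower than elimination (6 h against 2 h), the MRT version is 1 + 6/2 = 4.0 times true and the lambda_z version is 3.0 times true.

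**Day 7 Dose/AUC0-inf.** With fast input and x = 2^(-24/t), the ratio to true CL/F is (1 - x)/(1 - x^7):

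- 1.88 h: x = 0.0001, ratio 1.000
- 6.06 h: x = 0.064, ratio 0.936 (6% low)
- 9.02 h: x = 0.158, ratio 0.842 (16% low)

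Slower absorption adds to this: at 6.06 h with a 3 h absorption half-life the ratio is 0.883. Dose/AUC_tau on Day 7 gives 1.000 at all three half-lives with fast input, and 1.044 even at 36.67 h.

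**Day 1 AUC0-inf.** The last Day 1 sample is at 24 h. With a 1 h absorption half-life, the extrapolated share is 8% at 6.06 h, 18% at 9.02 h, 41% at 17.42 h and 66% at 36.67 h. With absorption half-life 9 h and elimination half-life 9.02 h, Day 1 CL/F comes out at 0.38 of its true value.

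**The case against.** The strongest reply is that PK definitions are deferred to a plan we have not seen, and that natural readings remove most of the harm. AUC0-inf and CL/F sit apart from the steady-state bullet, so they may be meant for Day 1, with CL_ss/F for Day 7. V_ss/F sits beside lambda_z and CL_ss/F in a bullet where the subscript marks repeat dosing, so it may simply mean (CL_ss/F)/lambda_z. The measures are descriptive, no inferential statistics are planned, and stopping criterion h uses AUC and C_max only.

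Most of this stands for clearance, where the gap is missing detail that the PK SAP may already fill. It does not rescue V_ss/F. A separate plan can rename the parameter but cannot make it estimable, and the lambda_z reading concedes that the listed name is wrong.

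Stronger readings are tempting and are not supported:

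- A reader might infer that volume will be overstated and Day 7 clearance understated. Neither formula is written, so both are conditional.
- A reader might set absorption equal to loss from hamster lung, where Table 1-1 gives half-lives of 60.95 to 74.16 "hours in low dose group and 152.20 - 182.59 hours in high dose group", and obtain 1 + 60.95/9.02 = 7.8-fold. In the same model, that absorption would give a terminal blood half-life near 61 h, whereas the longest in Table 1-1 is 36.67 h. The documents do not equate lung elimination with absorption into blood.
- A reader might use 17.42 h and 36.67 h to claim that Day 7 clearance is 38% or 62% too low (ratios 0.616 and 0.381). These are the tops of Day 1 ranges and imply 1.62- and 2.63-fold carry-over. Table 1-1 reports no accumulation over 7 days, and over 14 days only a tendency in medium-dose females.

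The remedy also has limits: V_z/F is still inflated when absorption is slow, and Day 1 AUC0-inf can rest largely on extrapolation.

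**Conclusion.** The point holds for V_ss/F. It is a named secondary outcome that inhaled-only, non-compartmental data cannot estimate, whatever the PK SAP says. Computed from MRT, it would be about 1.1 to 2 times the true value by formula (1.13 to 2.16 on the planned sampling times) for a 9.02 h elimination half-life and absorption half-lives of 1 to 9 h. Computed from lambda_z, it is a different parameter, V_z/F. These sizes rest on a one-compartment linear model and on hamster or assumed half-lives. The non-identifiability does not.

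The clearance part is a secondary clarification. Only if someone divides dose by Day 7 AUC0-inf is the result low: by about 0 to 6% at the hamster Day 7 half-lives and up to 16% at 9.02 h with fast absorption, and by more if the human half-life is longer or absorption slower. The documents do not say that this will be done.

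**What to change.** In the synopsis, Protocol 2.2.2 and SAP 4.2.2, replace V_ss/F with V_z/F = (CL_ss/F)/lambda_z from Day 7. Label it an apparent terminal-phase volume that is still inflated when absorption is slow or rate-limiting, and that is not to be read as V_ss.

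In the same lists, or by confirming that the separate PK SAP already says so, state that:

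- Day 7 clearance is CL_ss/F = Dose/AUC_tau, and never Dose/AUC0-inf from Day 7;
- Part B AUC0-inf and CL/F come from the Day 1 profile only, and are reported only when the extrapolated share of AUC is below a maximum fixed before results are seen.

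The cost is wording, with no extra samples or participants. One listed parameter changes its name, and some Day 1 CL/F values may not be reportable.
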